2. INTRODUCTION

Suvecaltamide (JZP385, formerly CX-8998 and MK-8998) is a potent, highly selective, state-dependent, negative modulator of low-voltage-activated T-type calcium channels (also known as Cav3 channels) that is being developed for once-daily treatment of moderate to severe residual tremor in PD.

2.1. Study Rationale

Tremor negatively impacts the ability to perform ADL and negatively impacts psychosocial functioning for patients with Parkinson's disease (PD) throughout the disease course. There are currently no pharmacotherapies specifically approved for treatment of tremor in PD.

Dopaminergic therapies (eg, levodopa/carbidopa) are considered the gold standard treatment for motor symptoms; however, tremor response to these pharmacotherapies is highly variable among patients with PD and often tremor remains inadequately controlled at tolerable doses. This suggests that the underlying pathophysiology for tremor in PD is multifactorial and likely differs from the other motor symptoms of PD. The challenge of adequately treating tremor in PD with the available pharmacotherapies coupled with the significant impact on patient quality of life highlights the considerable need for novel pharmacotherapeutic options for the treatment of tremor in patients with PD.

Suvecaltamide is a highly selective negative modulator of Cav3 channels that shows low nM potency against all 3 Cav3 isoforms. Cav3 channels are low-voltage-activated T-type calcium channels that are thought to modulate neuronal cell firing and are highly expressed in brain areas that are hypothesized to be important in PD, particularly the subthalamic nucleus, ventrolateral thalamus, and the cerebellar-thalamic-cortical circuit. Numerous lines of evidence suggest that the increased activation of Cav3 channels and excessive rhythmicity play a key role in neurological disorders such as tremor in PD. Given that Cav3 channels are distributed in regions implicated in the pathophysiology of tremor and have been a pharmacological target in PD, selective targeting of these channels may offer an efficacious and well-tolerated treatment option.

The current study is designed to evaluate the efficacy and safety of suvecaltamide for the treatment of moderate to severe residual tremor in adults with PD that is not adequately controlled by PD medications and that interferes with their ADL and/or with their performance of tasks. [REDACTED]

[REDACTED] Representative of the real-world setting, a flexible-dosing regimen based on investigator assessment of clinical response and tolerability will be used. The flexible-dosing regimen further provides a conservative approach for the first larger study in the older PD population who may have other comorbidities and who are also taking PD medications, by starting suvecaltamide in patients at a lower dose and gradually titrating based on clinical response and tolerability.

2.2. Background

2.2.1. Parkinson's Disease

Parkinson's disease is a neurodegenerative disease affecting over 1 million patients in the United States, 1.2 million in Europe, and 6.3 million worldwide (Dorsey, 2018). The prevalence of PD is approximately 1% for individuals over 65 years of age, increasing to 3% for octogenarians (Nussbaum and Ellis, 2003).

PD is characterized early on by the classic motor symptom triad of resting tremor, bradykinesia, and rigidity (Postuma, 2015). Tremor is one of the most prominent and visible features of PD and is often the first symptom noticed by patients (Jankovic, 2008). Approximately 75% of patients with PD experience tremor at some point during the disease course (Hughes, 1993; Gupta, 2020). While rest tremor is commonly observed, the majority of patients also experience action and postural tremors (Pasquini, 2018; Gupta, 2020).

In addition to being one of the most visual symptoms of PD, tremor is also ranked as one of the 5 most troubling symptoms by both early and advanced stage patients (Politis, 2010), interfering with the ability to perform ADL and negatively impacting psychosocial functioning, including personal and social relationships, self-image, and overall sense of well-being (Heusinkveld, 2018).

There are currently no pharmacotherapies specifically approved for the treatment of tremor in patients with PD. Unlike other motor symptoms of PD, tremor often does not resolve for many patients despite treatment with standard PD medications including dopaminergic therapies (Yahr, 1969; Helmich, 2018). In addition, higher doses of these therapies are generally needed to address tremor symptoms. As a result, the dose-limiting side effects of nausea, vomiting, dyskinesia, or psychosis can lead to the undertreatment of tremor symptoms (Nonnekes, 2016). Taken together, the pharmacological treatment of tremor in patients with PD remains challenging and coupled with the significant impact on patient quality of life, there is a high unmet need for novel therapeutic options for the treatment of tremor in patients with PD.

2.2.2. Suvecaltamide

Suvecaltamide, a highly selective negative modulator of low-voltage-activated CaV3 channels, shows low nM potency against all 3 CaV3 isoforms. All 3 isoforms of CaV3 are expressed throughout the CNS and the peripheral nervous system. In particular, CaV3 channels are highly expressed in thalamocortical circuitry and tremor network regions, where they mediate subthreshold oscillations and excessive rhythmicity in pathophysiologic states found in movement disorders, such as essential tremor (ET) and PD, neuropathic pain, and epilepsy (Handforth, 2005; Llinás, 2007; Park, 2013). For example, Cav3 is highly expressed in brain areas that are hypothesized to be important in tremor in PD, particularly the STN, ventrolateral thalamus, and the cerebellar-thalamic-cortical circuit (Park, 2013). Consistent with these findings, pharmacological inhibition of Cav3 channels in the STN rescues locomotor deficits in rat models of PD (Tai, 2011). In clinical studies, zonisamide and topiramate, which are both thought to act, in part, through suppression of Cav3 activity, have shown some efficacy in patients with PD. However, their usefulness has been limited by poor tolerability and/or excessive premature discontinuations of treatment, potentially due to pharmacological activity on other types of ion channels (Morita, 2005; Ondo, 2007; Chang, 2015). Given that Cav3 channels

are distributed in regions implicated in the pathophysiology of tremor and have been a pharmacological target in PD, selective targeting of these channels may offer a more efficacious and better-tolerated treatment option.

A detailed description of the chemistry, pharmacology, efficacy, and safety of suvecaltamide is provided in the IB.

2.3. Benefit/Risk Assessment

2.3.1. Risk Assessment

Participants with tremor in PD who enroll in this study may encounter the following potential risks:

- The potential risks from treatment with suvecaltamide in participants with PD are expected to be consistent with the known pharmacology and safety profile of suvecaltamide in clinical studies conducted to date. In general, AE profiles were consistent across populations studied (eg, ET, schizophrenia, healthy volunteers).

Generally, the most commonly reported AEs were in the SOCs of Nervous System Disorders and Psychiatric Disorders and included dizziness, euphoric mood, headache, and insomnia. Most AEs were mild or moderate in severity, were transient, and did not lead to study discontinuation. No clinically important trends in vital signs, safety laboratories, or ECG parameters have been observed in the completed clinical studies.

- The potential risks to participants with PD will be managed and mitigated by the use of exclusion criteria in this clinical study protocol, which will preclude participants with an unstable or clinically significant medical condition, or who are at significant risk for cardiovascular complications, suicide, or drug abuse from participating in the studies. In addition, a flexible-dosing regimen and titration schedule will be implemented such that participants will start at a lower dose and titrate up to an individually optimized dose based on tolerability and efficacy. This will help mitigate the potential risk associated with pharmacodynamic interaction between suvecaltamide and concomitant PD medication. Extensive monitoring of AEs, ECGs, orthostatic hypotension, and suicidal ideation and behavior will occur at frequent clinic visits throughout the study. These measures are intended to mitigate potential risks and to more fully assess the risks of using suvecaltamide for this indication.

- For participants who are randomized to receive placebo, the risks may be similar to the risks associated with uncontrolled or inadequately controlled tremor in PD, however, these risks are not worse than the risks faced by the PD population treated according to standard of care. The consequences of inadequately controlling tremor in PD include decreased work productivity, increase psychosocial burden, as well as functional limitations resulting from motor impairment (eg, the inability to attend to personal needs and perform personal hygiene activities), all of which contribute to an overall reduction in quality of life.
- Study procedure-related risks, including risks and/or discomfort associated with blood collection, ECGs, physical examinations, and completion of questionnaires and other assessments (see [Section 8](#) for details of study assessments).

2.3.2. Benefit Assessment

Participants with tremor in PD who enroll in this study may experience the following benefits:

- Treatment with suvecaltamide for the study duration may alleviate the significant symptom burden associated with tremor in PD.
- Irrespective of which treatment a participant receives in the study, all participants will contribute to the process of developing new therapies in tremor in PD.
- Participants will receive comprehensive clinical exams and clinical monitoring associated with the study for up to 23 weeks.

2.3.3. Overall Benefit:Risk Summary

Benefits to participants include the potential to receive therapy which may alleviate symptoms of tremor in PD, contribute to the development of new therapeutics in tremor in PD, as well as receiving comprehensive physical examination, clinical safety assessments, and laboratory testing.

Risks to participants include those related to suvecaltamide, the potential to be treated with placebo for the study duration, potential pharmacodynamic interactions between suvecaltamide and concomitant PD medications, and risks related to the study procedures including blood collection. The remaining risks associated with treatment with suvecaltamide are expected to be like those seen in previous clinical studies (see [Section 2.3.1](#)).

More detailed information about the known and expected benefits and risks and reasonably anticipated AEs of suvecaltamide may be found in the IB and Development Safety Update Report.

3. OBJECTIVES, ESTIMANDS, AND ENDPOINTS

Table 5: Primary and Key Secondary Objectives and Estimands

Objectives	Estimands and Attributes
Primary 
To evaluate the efficacy of suvecaltamide administered once daily for 17 weeks to improve functional and performance-based impairment due to tremor.
	
Treatments: Suvecaltamide and placebo.
 
Population: Participants with PD who are experiencing moderate to severe residual tremor despite being optimally treated on a stable regimen of PD medication(s).
 
Variable: Change from Baseline to Week 17 on the TETRAS composite outcome score.^a
 
Intercurrent events: Alternative/additional therapy as well as discontinuation of treatment due to lack of efficacy, an AE, or any other reason. Definitions for all intercurrent events are provided in Section 9.4.1.3. Participants who experience any intercurrent event will be included in the analysis regardless (treatment policy).
 
Summary: Difference in the mean change in the TETRAS composite outcome score^a from Baseline to Week 17 between suvecaltamide and placebo.

Key Secondary 
To evaluate the efficacy of suvecaltamide administered once daily for 17 weeks to improve functional impairment due to tremor.
	
Treatments: Suvecaltamide and placebo.
 
Population: Participants with PD who are experiencing moderate to severe residual tremor despite being optimally treated and on a stable regimen of PD medication(s).
 
Variable: Proportion of participants who improved (\geq 1-point improvement) from Baseline to Week 17 on the CGI-S.
 
Intercurrent events: Alternative/additional therapy as well as discontinuation of treatment due to lack of efficacy, an AE, or any other reason. Definitions for all intercurrent events are provided in Section 9.4.1.3. Participants who experience any intercurrent event will be included in the analysis regardless (treatment policy).
 
Summary: Difference in the proportion of participants who improved (\geq 1-point improvement) from Baseline to Week 17 in CGI-S scores between suvecaltamide and placebo.

Abbreviations: AE = adverse event; CGI-S = Clinical Global Impression of Severity; PD = Parkinson's disease; TETRAS-ADL = The Essential Tremor Rating Scale, Activities of Daily Living Subscale; TETRAS-PS = The Essential Tremor Rating Scale, Performance Subscale.

^a The TETRAS composite outcome score is the sum of modified items 1 to 11 of the TETRAS-ADL and items 6 (6a and 6b) and 7 of the TETRAS-PS. For TETRAS-ADL, each item is modified from 5 response items to 4 response items by collapsing options 0 and 1 together. For TETRAS-PS, each item is modified from 9 response items (due to 0.5 scoring increments) to 4 response items.

Table 6: Secondary and Exploratory Objectives and Endpoints

Objectives	Endpoints
Secondary	
To evaluate the efficacy of suvecaltamide administered once daily for 17 weeks to improve tremor and the functional impairment due to tremor.	
 • Change from Baseline to Week 17 on TETRAS-ADL.^a • Change from Baseline to Week 17 on TETRAS total score (TETRAS-ADL + TETRAS-PS).^a • Proportion of participants who improved (≥ 1 point) from Baseline to Week 17 on the PGI-S. • Proportion of participants who were much improved on the PGI-C at Week 17. • Proportion of participants who were much improved on the CGI-C at Week 17. • Change from Baseline to Week 17 on TETRAS-PS.^a • Change from Baseline to Week 17 on the MDS-UPDRS tremor score (items 2.10, 3.15, 3.16, 3.17, and 3.18).
To evaluate the safety and tolerability of suvecaltamide administered once daily for 17 weeks.	Incidence and severity of AEs as well as evaluation of safety laboratory assessments, vital signs, ECG results, C-SSRS, and QUIP-RS.

Objectives	Endpoints
	█ ██████████
█ █	█ ██████████ █ ██████████ █ ██████████ █ ██████████
█ █ █ █	█ ██████████ █ █ █ ██████████ █ ██████████ █ ██████████

Abbreviations: AUC = area under the plasma concentration-time curve; CGI-C = Clinician's Global Impression of Change; C-SSRS = Columbia Suicide Severity Rating Scale; C_{\max} = concentration at peak; C_{τ} = concentration at trough; ECG = electrocardiogram; █ MDS-UPDRS = Movement Disorder Society Unified Parkinson's Disease Rating Scale; PD = Parkinson's disease; █ PGI-C = Patient's Global Impression of Change; █ PGI-S = Patient's Global Impression of Severity; █ QUIP-RS = Questionnaire for Impulsive-Compulsive Disorders in Parkinson's Disease Rating Scale; █ $t_{1/2}$ = terminal half-life; █ TETRAS-ADL = The Essential Tremor Rating Scale, Activities of Daily Living Subscale; TETRAS-PS = The Essential Tremor Rating Scale, Performance Subscale; T_{\max} = time to maximum concentration.

^a This endpoint uses the unmodified or raw TETRAS score.

^b For the modified items 1-11 of the TETRAS ADL, each item is modified from 5 response items to 4 by collapsing options 0 and 1 together.

^c For the modified items 6 (6a and 6b) and 7 of the TETRAS PS, each item is modified from 9 response items (due to scoring in 0.5 increments) to 4 response items.

4. STUDY DESIGN

4.1. Overall Design

This is a 17-week double-blind, placebo-controlled, randomized, flexible-dosing, parallel-group, multicenter study of the efficacy and safety of suvecaltamide in the treatment of moderate to severe residual tremor in adult participants with PD. [REDACTED]

The maximum total duration of the study for each participant will be 23 weeks, with a maximum treatment duration of 17 weeks. For each participant, the study consists of a Screening Period (up to 4 weeks), a 5-week Dose Titration and Optimization Period, a 12-week Maintenance Period, and a 2-week Safety Follow-up Period. There is no continued access to study intervention upon completion of the study.

During the Screening Period, all participants will be evaluated for eligibility (including an assessment of their concomitant PD medication use) and will washout any prohibited medications. Participants may be allowed to rescreen once if the rescreening is approved by the Sponsor Medical Monitor.

Participants eligible for the study will be randomized 1:1 to receive suvecaltamide or placebo and stratified by TETRAS composite outcome score (≤ 17 or > 17) as assessed at Baseline.

Suvecaltamide (or matching placebo) will be administered orally [REDACTED] [REDACTED]. Each participant's optimal dose (10, 20, or 30 mg suvecaltamide or matching placebo) will be determined by the investigator during the Dose Titration and Optimization Period, and the participant will receive this optimal dose throughout the Maintenance Period as follows:

- Dose Titration and Optimization Period: study intervention will be titrated by the investigator in collaboration with the participant to individually optimize efficacy and tolerability. Every effort should be made by the investigator to ensure that the maintenance dose is optimized for efficacy and tolerability. Investigators should thoroughly assess whether tremor symptoms have been optimally treated and consider up-titration if therapeutic benefit has not yet been achieved. The starting dose is 5 mg suvecaltamide or 1 matching placebo capsule once daily. After 7 to 14 days, the dose of study intervention will be increased to 10 mg suvecaltamide (or 1 matching placebo capsule) [REDACTED]

[REDACTED] [REDACTED]. If needed, participants will be able to titrate down to a minimum of 10 mg suvecaltamide (or a minimum of 1 matching placebo capsule) per day at any time following consultation with the investigator. Participants not tolerating a once-daily dose of 5 mg suvecaltamide after 2 weeks of treatment will be discontinued from the study.

- Maintenance Period: participants will continue to take study intervention of 1, 2, or 3 capsules of either suvecaltamide (10 mg per capsule) or matching placebo at the optimal dose determined by the investigator at the end of the Dose Titration and

Optimization Period (see [Table 7](#)). No dose adjustment should occur during the Maintenance Period. If the investigator determines a dose adjustment is indicated for safety reasons, the Medical Monitor should be consulted regarding continuation of study intervention.

A 2-week Safety Follow-up Period (with visit planned at the end of the 2-week period) will be required for participants who either discontinue early or fully complete the Maintenance Period.

Assessments of efficacy, safety, [REDACTED] will be conducted as described in [Section 8.2](#), [Sections 8.3/8.4](#), and [Section 8.5](#), respectively, and as described in the SoA ([Section 1.3](#)). Note that to ensure study intervention is taken in the morning, clinic visits should take place in the morning.

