[REDACTED] SV = Screening Visit; TETRAS-ADL = The Essential Tremor Rating Scale, Activities of Daily Living Subscale; TETRAS-PS = The Essential Tremor Rating Scale, Performance Subscale; W = week; WOCBP = women of childbearing potential.

^a Discontinuation from study intervention does not represent discontinuation from the study. For participants who discontinue study intervention early, every effort should be made to attend Efficacy Follow-up Visits through 17 weeks after the first dose. See [Section 7](#) for additional guidance.

^b If participant discontinues study intervention early (regardless of whether or not he/she continues in the study), he/she will require an E/D Visit and a Safety FU Visit. The E/D Visit should occur as soon as possible following early discontinuation of study intervention. The Safety FU Visit should occur 2 weeks after the E/D visit.

^c Additional onsite clinic visits may be scheduled at any time, including in place of scheduled phone contacts, if required due to local requirements (eg, for study intervention dispensation). If performed in-clinic, urine pregnancy testing should be completed for WOCBP.

^d Clinic visits at Week 1, Week 2, Week 5, Week 9, Week 13, E/D, and Safety FU may be conducted remotely, if required due to the coronavirus 2019 pandemic, and with approval from the Sponsor Medical Monitor. The TETRAS-PS and MDS-UPDRS will not be performed during remote visits [REDACTED]
[REDACTED]

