7.1.1. Participants Remaining in the Study After Study Intervention Discontinuation

Discontinuation from study intervention does not represent discontinuation from the study. For participants who discontinue study intervention early, every effort should be made to attend Efficacy Follow-up Visits through 17 weeks after the first dose of study intervention. After completing the E/D visit, if the participant is willing to attend Efficacy Follow-up Visits after the study intervention is discontinued, the guidelines for scheduling efficacy visits are as follows:

- For participants who discontinue study intervention prior to the Week 9 Visit, it is encouraged to schedule 3 additional Efficacy Follow-up Visits at 9, 13, and 17 weeks after first dose.
- For participants who discontinue study intervention after the Week 9 Visit but prior to the Week 13 visit, it is encouraged to schedule 2 additional Efficacy Follow-up Visits at 13 and 17 weeks after first dose.
- For participants who discontinue study intervention after the Week 13 Visit but prior to the Week 17 Visit, it is encouraged to schedule an additional Efficacy Follow-up Visit at 17 weeks after first dose.
- Participants should be scheduled for the Safety Follow-up Visit 2 weeks after the last dose of study intervention. However, 1 of the Efficacy Follow-up Visits can be combined with the participant's Safety Follow-up Visit if the Efficacy Follow-up Visit is scheduled to occur within 2 weeks after the participant's last dose of study intervention.

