7.2. Participant Discontinuation/Withdrawal from the Study

- A participant may withdraw from the study at any time at his/her own request or may be withdrawn at any time at the discretion of the investigator for safety, behavioral, or compliance reasons.
- At the time of discontinuing from the study, an E/D Visit should be conducted. In addition, a Safety Follow-up Visit should be conducted as shown in the SoA ([Section 1.3](#)). See the SoA for data to be collected at the time of study discontinuation and at the Safety Follow-up Visit and for any further evaluations that need to be completed. The participant will be permanently discontinued both from the study intervention and from the study at that time.
- If the participant withdraws consent for disclosure of future information, the sponsor may retain and continue to use any data collected before such a withdrawal of consent.
- If a participant withdraws from the study, he/she may request destruction of any samples taken and not tested, and the investigator must document this in the site study records.

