**Table 5: Study Intervention**

Arm	Dose Regimen
Placebo	1, 2, or 3 placebo capsule(s) QD, oral
JZP385	1, 2, or 3 × 10mg capsule(s) mg QD, oral

The starting dose is 5 mg JZP385, or 1 matching placebo capsule once daily. After 7 to 14 days, the dose of study intervention will be increased to 10 mg JZP385 (or 1 matching placebo capsule) per day for 7 days. Titration may proceed at a rate of 10 mg JZP385 (or 1 matching placebo capsule) per day every 7 days as required for optimal efficacy and tolerability up to a maximum dose of 30 mg JZP385 (or 3 matching placebo capsules) per day. If needed, participants will be able to titrate down to a minimum of 10 mg JZP385 (or a minimum of 1 matching placebo capsule) per day at any time following consultation with the investigator. Participants not tolerating a once-daily dose of 5 mg JZP385 after 2 weeks of treatment will be discontinued from the study.

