**Table 7: Visit Windows Mapping for Assessments**

Study Period	Scheduled Visit	Target Study Day	TETRAS-ADL /TETRAS-PS, PGI-S/CGI-S, MDS-UPDRS	PGI-C/CGI-C	█████████████████████ Weight, ██████████ QUIP-RS	Chemistry, Hematology, Urine Drug Screening	Temperature and Respiratory rate, Urinalysis Labs	ECG	Blood Pressure and Pulse, C-SSRS
Screening	Screening	na	Any Day up to -2	na	Any Day up to -2	Any Day up to -2	Any Day up to -2	Any Day up to -2	Any Day up to -2
Baseline	Baseline	-1	Closest prior to dosing	na	Closest prior to dosing	Closest prior to dosing	Closest prior to dosing	Closest prior to dosing	Closest prior to dosing
DTOP	Week 1	7	na	na	na	na	1 – 20	1 – 34	1 – 10
	Week 2	14	na	na	na	na	na	na	11 – 20
	Week 5	35	1 – 48	na	na	1 – 48	21 – 48	na	21 – 48
MTP*	Week 9	63	49 – 76	1 – 76	na	49 – 76	49 – 76	35 – 90	49 – 76
	Week 13	91	77 – 104	77 – 104	na	77 – 104	77 – 104	na	77 – 104
	Week 17	119	105 – End of MTP	105 – End of MTP	36 – End of MTP [**or >36 and not SFU visit]	105 – End of MTP	105 – End of MTP	91 – End of MTP	105 – End of MTP
SFUP	Safety Follow-up	na	Nominal SFU visit	na	Nominal SFU visit [weight and QUIP-RS only]	Nominal SFU visit	Nominal SFU visit	Nominal SFU visit	Nominal SFU visit

Abbreviations: CGI-C = Clinician's Global Impression of Change; C-SSRS = Columbia Suicide Severity Rating Scale; DTOP = Dose Titration and Optimization Period; ECG = electrocardiogram; [REDACTED] MDS-UPDRS = Movement Disorder Society Unified Parkinson's Disease Rating Scale; MTP = Maintenance Period; PGI-C = Patient's Global Impression of Severity; PGI-S = Patient's Global Impression of Change; [REDACTED] QUIP-RS = Questionnaire for Impulsive-Compulsive Disorders in Parkinson's Disease Rating Scale; [REDACTED] SFUP = Safety Follow-up Period; TETRAS = The Essential Tremor Rating Scale.

\* In case of early discontinuation, Efficacy follow-up visits will be considered as scheduled visit, see Protocol, Section 7.1.1

\*\* For participants who don't enter the MTP, assessments (different from safety follow-up) occurring 36 days post first dose date will be mapped to Week 17.

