#### 4.1.3. Intercurrent Events Strategies

For the primary and key secondary estimands analysis, the following ICEs should be considered:

- Treatment discontinuation due to lack of efficacy or an AE; and any other reasons including study treatment noncompliance.
- Additional/alternative therapies used after the first dose of study intervention including PRN use of PD medications, switching PD treatments, or any dose/regimen change of background PD treatments.

The ICEs will be handled using 2 approaches:

[figure not shown]
- For the main analytical approach, the treatment policy strategy will be used to address all defined ICEs. The treatment policy strategy is defined as the effect of the randomized intervention over the study period regardless of the occurrence of an intercurrent event. Per the treatment policy, data should be collected after the occurrence of intercurrent event and will be included for statistical analyses and data interpretation.
- For the supplemental analysis approach, hypothetical strategy will be used to address post-ICE observations up to Week 17 due to discontinuation of study treatment. For ICEs of additional/alternative therapies used after the first dose of study treatment, treatment policy should still be applied. The hypothetical strategy is defined as the pharmacologic effect of JZP385 compared to placebo assuming the intercurrent event did not happen with continuation of randomized treatments for the duration of the study. Analysis will be conducted using data collected at time points that are obtained at or prior to participants discontinuing from study treatment and combined with modeled values for post-discontinuation timepoints where the underlying assumptions are considered as appropriate.

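### Participants who cannot tolerate the 5 mg starting dose are removed from the study, against the protocol's own follow-up rule and the treatment-policy estimand

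*Protocol*

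**What the plan says.** Two rules apply to the same event.

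- **Removal.** Protocol 4.1, on the Dose Titration and Optimization Period: "Participants not tolerating a once-daily dose of 5 mg suvecaltamide after 2 weeks of treatment will be discontinued from the study". SAP 1.2.2 says the same: "Participants not tolerating a once-daily dose of 5 mg JZP385 after 2 weeks of treatment will be discontinued from the study". Protocol 7.2 describes what leaving the study means: an Early Discontinuation (E/D) Visit and a Safety Follow-up Visit are done, and "The participant will be permanently discontinued both from the study intervention and from the study at that time".
- **Retention.** Protocol 7.1.1: "Discontinuation from study intervention does not represent discontinuation from the study". Footnote a of the Schedule of Activities adds: "For participants who discontinue study intervention early, every effort should be made to attend Efficacy Follow-up Visits through 17 weeks after the first dose". For a stop before Week 9, Section 7.1.1 encourages visits at Weeks 9, 13 and 17. Neither place makes an exception for intolerance of 5 mg. SAP Table 7 relies on this rule: "In case of early discontinuation, Efficacy follow-up visits will be considered as scheduled visit, see Protocol, Section 7.1.1".

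Protocol Section 3 (Table 5) lists stopping treatment for lack of efficacy, an AE or any other reason as an intercurrent event, handled by treatment policy for both tested estimands. SAP 4.1.3 draws the consequence: "Per the treatment policy, data should be collected after the occurrence of intercurrent event and will be included for statistical analyses and data interpretation".

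**The concern.** Treatment policy needs outcomes observed after treatment stops. The removal rule ends efficacy follow-up for one group defined by poor tolerability of the starting dose. Under Protocol 9.4.1.5 and SAP 4.1.4 the main analysis then treats their later scores as missing at random. They are modelled like completers in the same arm and stratum with a similar early course. A participant who took 5 mg for about two weeks and stopped is unlikely to keep the benefit of a completer on 10 to 30 mg. If such exits are more frequent on suvecaltamide, the estimate moves in favour of the drug. The same gap arises for the CGI-S responder endpoint, where multiple imputation makes a similar assumption.

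**Working it through.** **1. Which text governs.** Protocol 7.1 lists an AE among the reasons to stop study intervention, not to leave the study. Protocol 7.2 allows withdrawal at the participant's request or the investigator's discretion, whereas 4.1 is mandatory. No passage says which rule yields. The conflict is limited to participants still not tolerating 5 mg after two weeks. Those who stop earlier, or at 10 mg or more, already fall under 7.1.1.

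**2. What data remain under the removal rule.** The E/D Visit collects TETRAS-ADL, TETRAS-PS and CGI-S. SAP Table 7 maps Days 1 to 48 to Week 5, so an E/D Visit shortly after Week 2 becomes a Week 5 value. If that visit is remote (footnote d), TETRAS-PS is not done and there is no composite. The Safety Follow-up Visit adds TETRAS-ADL but not TETRAS-PS, so it gives no composite either. Weeks 9, 13 and 17 are missing.

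**3. The plan's own figures (SAP Section 5).** With a difference of 3.0, SD 6.0, two-sided 0.05 and a two-sample t-test, the required size is 63.8, so 64 per arm, with 80.1% power. Dropout: 64 / (1 − 0.20) = 80 per arm, 160 in total. Both agree with the SAP. The planned standard error is 6 × √(2/64) = 1.06.

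**4. Size of the overstatement.** The documents give none of the following, so they are assumptions:

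- *f*, the share of the active arm removed: 1% to 10% (about 1 to 8 of 80)
- no drug effect in this group at the E/D Visit or at Week 17
- *d5*, the Week 5 effect in those who continue: 1.5 to 3.0 points
- *b*, the slope of the Week 17 score on the Week 5 score: 0.5 to 0.7

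The treatment-policy effect is 3.0 × (1 − f). If the model credited the removed group with the full effect, the overstatement would be 3.0 × f, which is a ceiling. Because the MMRM uses the E/D score as the Week 5 value, its estimate is 3.0 − b × f × d5. The overstatement is then

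3.0 − b·f·d5 − 3.0(1 − f) = f × (3.0 − b × d5).

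The factor in brackets runs from 3.0 − 0.7 × 3.0 = 0.9 to 3.0 − 0.5 × 1.5 = 2.25.

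| f | Ceiling, points (share of SE) | With E/D score, points (share of SE) |
|---|---|---|
| 1% | 0.03 (3%) | 0.01 to 0.02 (1% to 2%) |
| 2.5% | 0.075 (7%) | 0.02 to 0.06 (2% to 5%) |
| 5% | 0.15 (14%) | 0.05 to 0.11 (4% to 11%) |
| 10% | 0.30 (28%) | 0.09 to 0.23 (8% to 21%) |

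A simulation of 20,000 trials with 80 per arm agrees. At f = 10%, b = 0.5, d5 = 1.5, the mean estimate is 2.926 against 2.699 with full follow-up, an excess of 0.227 (formula 0.225). At f = 2.5%, b = 0.7, d5 = 3.0, the excess is 0.022 (formula 0.0225).

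**5. Power.** If these exits fall within the planned 20% dropout, nothing changes. If they come on top of it in both arms, power falls from 80.1% to 78.9% (2.5%, 62 per arm), 77.5% (5%, 60 per arm) or 74.6% (10%, 56 per arm).

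**The case against.** The strongest reply is that the sentence in 4.1 is loose wording. The Schedule of Activities sends sites to Section 7 on discontinuation, Section 7 separates stopping treatment from leaving the study, and 4.1 is a design overview. SAP 1.2.1 also speaks loosely of discontinuing the study early. This may well be what the sponsor means. But the protocol itself makes the distinction, 4.1 falls on the wrong side of it in mandatory terms, and a site could follow it as written.

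The second reply is that few people are affected. This stands. Protocol 2.3.1 reports that most AEs were mild or moderate, transient and did not lead to discontinuation. Protocol 4.2 says that in the earlier essential tremor study AEs came mainly in the first week, and most of the common ones resolved within a week of starting despite continued dosing. That study reached 16 and 20 mg a day, though not in Parkinson's disease. Intolerance of 5 mg lasting past two weeks should therefore be uncommon, and the lower rows of the table may be pessimistic.

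The third reply is that the analysis plan already allows for such exits. The Full Analysis Set keeps these participants. Control-based imputation covers AE and lack-of-efficacy exits, and a tipping-point analysis follows. SAP 4.2.4 requires these only if the primary result is significant, but that is when an overstatement would matter most. CGI-S has non-responder imputation and a two-dimensional tipping point without that condition. These analyses test the missing-at-random assumption. They do not supply the missing outcomes, and the main estimate stays as it is.

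**Conclusion.** The conflict is real and unresolved in the text. As written, the rule withholds data that both tested estimands call for, in a group selected on tolerability. The consequence is probably small: about 0.02 to 0.23 points, or 2% to 21% of the planned standard error, if 2.5% to 10% of the active arm is removed, and less at 1%. The ceiling at 10% is 0.30 points. These figures rest on assumed values of f, b and d5, on no lasting drug effect in those removed, and on an E/D composite score being obtained. Off-drug data from other discontinuers would lower them further. No planned figure for sample size or power is wrong. The point should be corrected because the rule contradicts the estimand and the correction is cheap, not because it is likely to change the trial's conclusion.

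**What to change.** In Protocol 4.1, replace removal from the study by: *discontinued from study intervention and followed per Section 7.1.1*. Make the same change in SAP 1.2.2 so that the documents agree. Send sites a short memo, since the protocol text and the memo govern conduct and the SAP sentence is only descriptive. Withdrawal under Section 7.2 stays available. Dose, stopping rule, 160 randomized and 64 evaluable per arm are unchanged.

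The cost is one phrase in each document, the memo, and up to three Efficacy Follow-up Visits (Weeks 9, 13 and 17) per willing participant, all already in the Schedule of Activities. The gain is limited because Section 7.1.1 only encourages these visits. If a share r of the group attends, roughly a share r of the overstatement is removed.
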